Study title: **Cardiac MRI for Metal on Metal Orthopaedic Prostheses**

List of Investigators:

- [name] (Principal Investigator),
- [name] (Co-Investigator)
- [name] (Co-Investigator)
- [name] (Co-Investigator)

NCT02892448

Document date: 06 Jul 2017

Abstract: There may be a relationship between heart function and the metal ION levels in patients having undergone total hip replacement. The idea is to use results from a clinical cardiac MRI to assess heart function in a sample of 20 patients whom have also undergone metal-on-metal hip replacement, and 10 patients who have had hip replacement surgeries without metal-on-metal implants, to determine whether having undergone this procedure may be impacting heart function. In addition to the clinically used parameters, the images will also be retrospectively assessed using special software to assess amount of fibrosis and early changes affecting cardiac muscle contraction which may be indicative of impaired heart function. With these values we will compare to known, and previously collected, hip replacement and function data to determine whether there is any differences in how the heart works in those having had a hip replacement relative to a normal population.

Hypothesis:

Cardiac function in patients with previous metal-on-metal hip replacement will inversely correlate to the metal ion levels in the blood.

Introduction:

There has been some recent concern regarding possible systemic health effects resulting from elevated blood cobalt concentrations in patients with cobalt containing hip implants (1). To date there are no blood cobalt criteria to help guide physicians when evaluating an individual hip implant patient's risk of developing systemic health effects because historically there was little or no concern about systemic cobalt toxicity in implant patients. Included within this is heart function, for which we see a need to use this novel software to analyze heart function relative to Hip status and Metal Ion levels.

Patients with metal on metal hip prosthesis are subject to local and systemic release of cobalt and chromium ions which may increase the potential for locally aggressive ion-induced local tissue reactions such as pseudotumours, a type of Adverse Reaction to Metal Debris (ARMD) (2). Although there have been reports of local toxicity as well as cases of cobaltism (as seen during outbreak in Quebec of so called 'cobalt beer drinkers' cardiomyopathy) leading to cardiac and ototoxicity, it is unclear if chronic exposure to these ions can lead to impaired cardiac function (cardiotoxicity) in a well-functioning prosthesis.

The majority of the blood cobalt concentrations reported for hip implant patients appear to range from approximately 0.2 to 10 µg/L, and based on our review of the available literature, should not pose an increased risk for the development of systemic health effects.

The concern for systemic health effects is for the small number of patients with cobalt-containing hip implants with markedly elevated blood cobalt concentrations.

Extensive evaluations of these 'cobalt beer drinkers' have found that poor nutrition and underlying disease states caused by severe alcoholism were likely significant contributing factors to heart disease in this particular population. However, there remains a significant concern that cardiac function could be

affected in the long term. This is especially relevant as the majority of these implants are put in patients less than 50 years age.

Cardiac magnetic resonance imaging (CMR) is the gold standard method to assess cardiac function in patients at risk of cardiotoxicity. In addition to assessing cardiac function, CMR enables imaging of inflammation, and fibrosis (which may be secondary to the ion deposition) in the heart which may provide more specific information about the mechanism of injury in these patients.

The purpose of this study is to look at cardiac function in patients with a metal on metal hip prostheses.

Recruitment: 30 patients in total (10 unilateral and 10 bilateral) will be recruited which should provide indication of relationship both between either instances and heart function, as well as compared to one another. As well, 10 Total Hip Arthroplasty patients (who would not have metal-on-metal implants) will be case-matched by body surface area and age at surgery to already-recruited participants in either the unilateral or bilateral metal-on-metal participants. This will be used as the Control Group, as there is no evidence of elevated metal ions in this population. All patients will be undergoing clinical cardiac MRI and have previously undergone Metal on Metal hip arthroplasty or a non-Metal on Metal total hip arthroplasty. All patients will have extra images collected during their MRI and these images will be analyzed to determine any relationship between heart function and the possible metal ion levels from the hip implant. As part of the scan analysis they will be required to also have a 5mL vial of blood collected. Ultrasound values will be retrospectively collected, for analysis of soft tissue reaction, from a previous clinically ordered Ultrasound of the affected joint. Participants will be asked to complete blood testing to determine heart health after the scan.

Inclusion/Exclusion Criteria:

Inclusion:

- Undergoing clinical Cardiac MRI
- Have either unilateral MoM Hip replacement device if in Unilateral Group OR bilateral MoM hip replacement devices if in Bilateral Group OR have a total hip non-MoM device if in Control Group
- Willing to sign Informed Consent Form

Exclusion:

- Patient does not meet all 'inclusion' criteria.

Procedures:

A clinically indicated cardiac MRI will be performed at baseline to evaluate RV/LV function. At each imaging session, a single 5 ml blood sample is required for measurement of the hematocrit, to be used in conjunction with the T1 measurements to ensure accurate estimation of extracellular volume (3).

The CMR examinations will be performed using a 1.5 Tesla scanner (Magnetom Aera , Siemens Healthcare, Erlangen, Germany) and a phased array coil. A standard MR-contrast kit containing one syringe of gadolinium-based contrast (Gadovist, Bayer Canada, Toronto, Canada.) and another with saline will be assembled for use in the MR power-injector. The technologist will attach the gadolinium line to the patient's angiocath and check for any air in the tubing. After performing standard scout views, vector ECG-gated steady-state free precession (SSFP) breath-hold cines in sequential 8 mm/2 mm in short-axis oblique and axial planes will be performed.

Myocardial oedema will be assessed by T2-weighted black blood imaging using turbo spin echo (TSE) acquisition in SAO, 4C, 2C, 3C views.

Cardiac T2\* imaging will be performed with a cardiac-gated, single-breath-hold, 8-echo sequence of a single midventricular short-axis slice. We will acquire T1 maps modified Look-Locker inversion recovery, "MOLLI" before administration of contrast to obtain native T1 values (4).

A single bolus of gadolinium (dose of 0.2 mmol per kilogram of body weight) followed by a saline flush by means of a power-injector will be administered for delayed enhancement imaging. We will perform standard phase-sensitive-inversion-recovery (PSIR) short axis oblique views starting 10 minutes after contrast administration.

15 minutes post-injection, we will again acquire post contrast T1 maps in short-axis oblique and four chamber views. T1 and T2 MyoMaps are approved by Health Canada. The commercial license number for MyoMaps on VE11 for a 1.5T system in Canada is 14441747.

Measurements of biventricular volumes, function and mass will be derived from the SSFP pulse sequence in the axial plane (RV) and short-axis plane (LV) on an Argus workstation (Siemens, Erlangen, Germany).

To determine if heart stress exists with these patients, we will also ask patients to consent to blood draws for 3 tests: a troponin test (determines heart stress via protein released when heart muscle is damaged), brain natriuretic peptide (BNP) test (checks for heart failure via a peptide that is released when there are pressure changes in the heart), and a biomarkers test. Each blood sample will consist of a 6mL tube. The biomarker tube will be held for up to 3 years for testing at the University of Ottawa Heart Institute.

#### Outcomes:

- Primary: A comprehensive cardiac function (i.e. right and left ventricular function, mass, volumes, fibrosis and heart health determined by blood tests) assessment by clinically indicated CMR. At the time of imaging, a single 5 ml blood sample will be required for measurement of the hematocrit, the latter will be used to perform post-hoc sophisticated analysis (such as T1 mapping) on the acquired MRI data sets for subclinical measures of cardiac dysfunction.
- Secondary: Cobalt and Chromium Ion level measurements in the blood as well as ultrasound of the hip to rule out soft tissue reaction.

#### Analyses:

Heart scan analyses:

We will generate pre-contrast and post-contrast T1 maps offline on an independent workstation. Following motion correction, we will compute T1 on pixel-by-pixel basis using non-linear curve fitting. Given the linear relationship between gadolinium contrast concentration and T1, we can estimate the change in contrast-concentration between pre- and post-Gd using the corresponding T1 maps. We can then estimate extracellular volume (ECV) from the difference between [Gd-DTPA] in the myocardium relative to the LV blood pool, calibrating for the hematocrit as follows: (5)

$$ECV = 1 - \text{hematocrit} \frac{\frac{1}{T1_{myopost}} - \frac{1}{T1_{myopre}}}{\frac{1}{T1_{bloodpost}} - \frac{1}{T1_{bloodpre}}}$$

We will determine the mean ECV for both LV and RV.

Finally, the phase contrast images of the aorta and main pulmonary artery will be analyzed to calculate flow, velocities, stroke volume and cardiac output.

Further Analyses: With the MRI results they will be compared to the Control Group to investigate how both unilateral and bilateral metal on metal implants may impact heart function in these patients. Significance will be set to P=0.05 for all findings.

Risks/Benefits: Standard of care in this situation would involve a standard cardiac MRI. In this case the patient will undergo 10 to 15 minutes more of scanning time to capture required images for analysis, as well as have a single 5mL vial of blood collected. Blood sample will be collected by certified staff.

- Risks: As the scan will only be 10 to 15 minutes longer than the typical cardiac MRI patients may experience minor discomfort due to laying still for this small extension during the scanning process. They may also experience mild pain, bruising, or infection at the site where blood is drawn.
- Benefits: Patients will not receive any direct benefit from their participation in this study. Their participation may allow the researchers to have a better understanding of how Metal on Metal Prostheses affect heart function, which may benefit future patients.

Patients may withdraw from the study at any time without any impact on their current or future care at this institution.

Patients are not waiving any legal rights by agreeing to participate in this study. The study doctor and the Ottawa Hospital still have their legal and professional responsibilities.

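### The printed ECV formula lacks brackets around 1 − hematocrit, so it gives 100% at zero myocardial uptake and, at a given hematocrit, falls as uptake rises

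*Combined protocol and SAP*

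**What the plan says.** Under Analyses (Heart scan analyses), the plan will "estimate extracellular volume (ECV) from the difference between [Gd-DTPA] in the myocardium relative to the LV blood pool, calibrating for the hematocrit". The equation that follows begins "ECV = 1 - \text{hematocrit" (shown here as machine-read markup). The next term is the fraction whose numerator is 1/T1 after contrast minus 1/T1 before contrast in myocardium, and whose denominator is the same difference in blood. No brackets enclose 1 − hematocrit. No other section gives a second version of the formula or a worked value.

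The result is used. The same section states: "We will determine the mean ECV for both LV and RV". Further Analyses adds: "With the MRI results they will be compared to the Control Group". Under Procedures, the hematocrit sample is "to be used in conjunction with the T1 measurements to ensure accurate estimation of extracellular volume". Under Outcomes, the primary outcome covers "right and left ventricular function, mass, volumes, fibrosis" and blood tests, and hematocrit feeds T1-mapping work "on the acquired MRI data sets for subclinical measures of cardiac dysfunction".

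**The concern.** By ordinary operator precedence the printed equation subtracts hematocrit times the ratio from 1. The plan's own description is of a different quantity: one built from myocardial contrast relative to blood, with hematocrit as a calibration. Such a quantity must be zero when the myocardium takes up nothing, and must rise as it takes up more. The printed equation does neither.

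ECV is the only measure for which the plan prints a formula, and no ECV software is named under Heart scan analyses. The equation is therefore the specification that a programmer or auditor would work from. Coded literally, it would put the wrong value on every LV and RV ECV with a ratio other than 1. It could also make the group with more contrast uptake appear to have the lower ECV.

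**Working it through.** **Notation.** H is hematocrit. R is the ratio of the two changes in 1/T1, myocardium over blood, as the equation defines it.

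- Printed: P = 1 − H × R
- Bracketed: B = (1 − H) × R

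**Algebra, with no assumed values.**

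1. At zero myocardial uptake, R = 0, so P = 1 (100%) and B = 0, whatever the hematocrit.
2. At fixed H, the slope in R is −H for P and +(1 − H) for B. The printed form falls as uptake rises.
3. P − B = 1 − HR − R + HR = 1 − R. The error depends on the patient's own ratio, so no constant offset removes it. P exceeds B whenever R is below 1, and the two agree only at R = 1.
4. The printed symbols can be grouped in two ways: 1 − (H × R) or (1 − H) × R. Only the second is zero at zero uptake and rises with uptake.

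**Size.** The documents give no T1, hematocrit or ECV values, so every input below is an assumption. At H = 0.42:

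| R | P = 1 − 0.42 × R | B = 0.58 × R | Difference, 1 − R |
|---|---|---|---|
| 0.45 | 81.1% | 26.1% | 55 points |
| 0.50 | 79.0% | 29.0% | 50 points |
| 0.60 | 74.8% | 34.8% | 40 points |

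Over H 0.35 to 0.50 and R 0.35 to 0.65:

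- P runs from 1 − 0.50 × 0.65 = 67.5% to 1 − 0.35 × 0.35 = 87.8%.
- B runs from 0.50 × 0.35 = 17.5% to 0.65 × 0.65 = 42.3%.
- The error runs from 65 down to 35 points.

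As an example from T1 values, take myocardium 1000 ms before and 450 ms after contrast, blood 1550 ms before and 300 ms after, and H = 0.40. Then R = (1/450 − 1/1000)/(1/300 − 1/1550) = 0.455, P = 81.8% and B = 27.3%. If post-contrast myocardial T1 is 400 ms, meaning more uptake, R = 0.558, P falls to 77.7% and B rises to 33.5%.

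**When the ordering reverses.** Hematocrit is measured per patient, and controls "will be case-matched by body surface area and age at surgery", not on hematocrit. Of two patients A and B, let B have the higher ratio. B gets the higher printed ECV only if H_B < H_A × R_A / R_B. Starting from H_A = 0.42 and R_A = 0.45:

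- R_B = 0.50: 0.42 × 0.45/0.50 = 0.378, which is 4.2 points below 0.42.
- R_B = 0.60: 0.42 × 0.45/0.60 = 0.315, which is 10.5 points below 0.42.

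Reversal is therefore not universal. For example, (H 0.50, R 0.45) against (H 0.35, R 0.50) gives B of 22.5% and 32.5%, and P of 77.5% and 82.5%, in the same order.

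**Simulation.** Two sets of runs, both on assumed distributions:

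- Pairs of patients, H and R uniform and independent over the ranges above, 2,000,000 draws: order reversed in 70.5%. It is reversed in 93.3% when hematocrit differs by at most 2 points, and in 100% at equal hematocrit.
- Groups of 10 against 10, mean R 0.50 against 0.45 (SD 0.05), mean H 0.42 in both (SD 0.035), 200,000 runs: expected difference 0.58 × 0.05 = +2.9 points bracketed and −0.42 × 0.05 = −2.1 points printed. Reversal here means a positive bracketed and a negative printed difference. It occurs in 93.8% of runs at equal mean hematocrit, 82.2% if the higher-ratio group's mean hematocrit is 2 points lower, and 36.6% if it is 5 points lower.

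**The case against.** The strongest reply is that the whole defect is one pair of brackets in one displayed equation that was machine-read from a PDF. The nested fractions and subscripts came through, but that does not prove every bracket did. If the brackets are on the source page, the point falls away. This cannot be settled from the text, so the finding is limited to the formula as printed.

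Second, the intended meaning can be recovered. The plan's description gives the right direction and the equation carries a literature reference. An analyst would probably question ECV values near 80% at the first patient. This makes silent propagation less likely, but the documents do not say how ECV is coded, and a plan should not rely on its reader to correct it.

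Third, the description fixes the zero point and the direction, not the exact form of the calibration. That is true. The bracketed form is inferred as the only grouping of the printed symbols that meets both conditions.

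Fourth, the scope is limited. ECV bears on the fibrosis part of a broad primary outcome. Ventricular function, mass, volumes, delayed enhancement and the blood tests are unaffected. ECV could also be recomputed from retained T1 maps and hematocrit without new patient data. All of this stands. It limits the severity but does not make the equation right.

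**Conclusion.** The concern holds as stated: the printed equation contradicts the plan's own description of ECV and gives a wrong result if followed. The values at zero uptake, the sign of the slope and the error of 1 − R are exact. The percentages rest on assumed hematocrit and ratio values, and the reversal rates also on assumed distributions and independence. Any harm requires literal coding. A reversed comparison with controls is likely when hematocrit is similar between groups and not assured otherwise. The point should be fixed, with medium confidence because the source page has not been seen.

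**What to change.** Check the source page first. If the brackets are absent there, print:

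ECV = (1 − hematocrit) × [(1/T1myo_post − 1/T1myo_pre) / (1/T1blood_post − 1/T1blood_pre)]

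Whether or not the page needs correcting, confirm that the implemented calculation returns 0 when myocardial T1 does not change between the pre- and post-contrast maps.

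As an editorial matter only, the sentence leading into the equation should say that contrast concentration is linear in 1/T1 rather than in T1. The equation already uses 1/T1, so no computed value changes.

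The cost is one equation, one phrase and one check of the analysis code, with no effect on patients or scanning.

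### The only labelled hypothesis, an inverse ion-function correlation in metal-on-metal patients, has no specified test: the Analyses section uses no ion level and compares only with controls

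*Combined protocol and SAP*

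**What the plan says.** All places are in the combined protocol and SAP.

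- **Hypothesis.** This is the only statement labelled as one: "Cardiac function in patients with previous metal-on-metal hip replacement will inversely correlate to the metal ion levels in the blood".
- **Introduction.** Two factors are to be studied; the stated need is "to use this novel software to analyze heart function relative to Hip status and Metal Ion levels".
- **Abstract.** A separate aim concerns the operation itself: "to determine whether having undergone this procedure may be impacting heart function".
- **Recruitment.** There are 10 unilateral MoM, 10 bilateral MoM and 10 non-MoM control patients. An ion analysis is announced: "All patients will have extra images collected during their MRI and these images will be analyzed to determine any relationship between heart function" and ion levels. Controls are justified by the absence of evidence that their ions are raised.
- **Outcomes.** The primary outcome is a list: right and left ventricular function, mass, volumes, fibrosis and blood tests. Cobalt and chromium levels are a secondary outcome. Nothing links the two.
- **Analyses.** After the T1, extracellular-volume and flow computations, the only comparison between patients is: "With the MRI results they will be compared to the Control Group to investigate how both unilateral and bilateral metal on metal implants" may affect heart function. The threshold is P=0.05 for all findings. Ion level does not appear in this section.

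**The concern.** A statement about correlation needs an analysis that uses both variables. Here the exposure variable is missing from the section that says what will be analysed. Someone who followed that section exactly would finish the study without testing its hypothesis.

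Two misreadings could follow. If the team runs the ion analysis announced under Recruitment, it must choose the measure, the ion and the type of correlation, and nothing requires that choice before the data are seen. A significant correlation could then be the best of many. If the team instead reports only the MoM-versus-control comparison, a difference could be presented as support for the ion hypothesis, although it says nothing about whether function declines with ion level among MoM patients.

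**Working it through.** The plan gives no sample-size, power or effect-size figure, so there is nothing of its own to reproduce. The main check is textual; the arithmetic shows what is at stake.

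**1. What a test of the hypothesis needs, and where it is found**

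| Element | Stated? | Where |
|---|---|---|
| Population | Yes: MoM patients, 10 + 10 = 20 | Hypothesis; Recruitment |
| Direction | Yes for function: inverse | Hypothesis |
| Cardiac variable | No: a list of measures | Outcomes |
| Ion | No: cobalt and chromium both listed | Outcomes |
| Type of correlation or model | No | – |
| Blood sample for the ion value | No: the tubes described are for hematocrit, troponin, BNP and biomarkers | Recruitment; Procedures |
| Place in the analysis section | No | Analyses |

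The stated direction fits ventricular function. Procedures describes troponin and BNP as markers of muscle damage and heart failure, so under the same hypothesis they would rise with ion level, as would fibrosis. One sign cannot serve the whole primary list.

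**2. False-positive chance if measure and ion are left open**

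Inputs: n = 20 MoM patients and P = 0.05 (documents). Two-sided testing is assumed. Seven measures are counted for illustration (RV function, LV function, mass, volumes, fibrosis, troponin, BNP), with two ions, so 7 × 2 = 14 tests.

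- If all 14 tests were independent: 1 − 0.95^14 = 0.512.
- They are not independent. Simulation of 40,000 null trials per setting, with Pearson tests, correlation between measures 0 to 0.5 and between ions 0.6 to 0.9 (all assumed), gives:

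| Named in advance | Chance of at least one p < 0.05 |
|---|---|
| Nothing (7 × 2) | 31–48% |
| Ion only (7 × 1) | 24–30% |
| Measure only (1 × 2) | 7–9% |
| Both (1 × 1) | 5% |

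**3. What one pre-named test in 20 patients can show**

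Fisher z, standard error 1/√(20 − 3) = 1/√17, two-sided 0.05:

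- Detectable |r| at 80% power: tanh((1.960 + 0.842)/√17) = tanh(0.680) = 0.591.
- 95% CI at observed r = 0: ± tanh(1.960/√17) = ± tanh(0.475) = ± 0.443.
- Power = Φ(atanh(r)·√17 − 1.960). At r = 0.3: Φ(1.276 − 1.960) = 25%. At 0.4: Φ(1.747 − 1.960) = 42%. At 0.5: Φ(2.265 − 1.960) = 62%.
- Adjusted for unilateral/bilateral status (partial correlation, √(20 − 4) = 4): detectable |r| = tanh(2.802/4) = 0.605.

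**The case against.** **The analysis is promised.** Recruitment says the images will be examined for a relation with ion levels and claims only an indication of relationship, not power. This stands in part: the analysis is unspecified, not abandoned. A reader might infer that the sponsor dropped the ion question; the documents do not support that.

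**The gap is narrower than it may seem.** The sentence under Recruitment covers all patients, so a reader might infer that the population is open (20 or 30) and the direction too. The Hypothesis section fixes the population as MoM patients and the direction for function. Both objections stand. What is missing is the variable, the ion, the method, the ion sample and a place under Analyses.

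**The control comparison does bear on ions.** Controls were chosen because raised ions are not expected in them. That stands: the contrast is an indirect, group-level proxy for exposure. A reader might infer either that it has nothing to do with ions or that it tests the hypothesis. Neither is right. Even perfect matching would not turn a group contrast into a correlation among MoM patients.

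**The count of seven is arbitrary.** It is. It counts volumes and mass once each and leaves out T2*, oedema, flow and the biomarker tube. The 31–48% is an illustration, not this protocol's error rate.

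**The repaired test is weak.** True, at 25–62% power for |r| of 0.3 to 0.5. Low power is a reason to state the precision, not a reason to leave the test undefined.

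**Conclusion.** The point holds and must be fixed. The sole labelled hypothesis has no specified test, and the one between-patient comparison that is specified answers the Abstract's separate question about the operation. This conclusion rests on the text alone and needs none of the assumed values.

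The size of the selection problem does rest on assumptions: roughly 31–48% against 5%, for seven measures, two ions and the correlations given above. The precision figures depend only on n = 20, two-sided 0.05 and the usual Fisher approximation.

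A reader might go further and put a figure on how often unmatched differences between MoM and control patients would imitate an ion effect. The documents give no ion distributions, standard deviations or offsets, so no such figure is offered.

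**What to change.** Add one paragraph under Analyses:

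- **Primary test of the hypothesis.** In the 20 MoM patients, the association of one single cardiac variable with one ion, both named before the data are seen. LV ejection fraction from the short-axis cines with log cobalt is one example; LV function alone is not one variable.
- **Method.** Name linear regression or Spearman correlation as primary and the other as sensitivity analysis. Report the estimate, 95% CI and two-sided p. Add a sensitivity analysis adjusted for unilateral/bilateral status, which may relate to both ion level and function.
- **Expected sign** for the named variable, noting that fibrosis, troponin and BNP would go the opposite way.
- **Ion sample.** State which blood sample, and its date, supplies the value. The Abstract's "known, and previously collected, hip replacement and function data" may include it but do not say so.
- **Status of the rest.** Other measures, the other ion and any pooled 30-patient analysis are exploratory. Keep MoM versus control for the Abstract's aim and say that it is not a test of the correlation.
- **Precision.** 80% power only for |r| of about 0.59; an observed r of 0 would not exclude a moderate correlation (95% CI about -0.44 to 0.44).

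**Cost.** One prior choice, one paragraph and a small set of analyses on outcomes already listed, with no added patients or scans. If no usable ion value exists, a further blood sample or a consent change may be needed. Power stays modest and falls further with adjustment for laterality, confounding among MoM patients is not removed, and the other measures lose confirmatory status.

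### The plan does not fix which result answers the study: the primary outcome is an unranked list, the ion hypothesis has no specified analysis, and 0.05 applies unadjusted to every finding

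*Combined protocol and SAP*

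**What the plan says.** - **Hypothesis:** "Cardiac function in patients with previous metal-on-metal hip replacement will inversely correlate to the metal ion levels in the blood". This is the only hypothesis stated.
- **Abstract:** the aim is also put as finding out "whether there is any differences in how the heart works in those having had a hip replacement relative to a normal population".
- **Recruitment:** "these images will be analyzed to determine any relationship between heart function and the possible metal ion levels from the hip implant". No ion, cardiac measure, patient set or test is named. The section plans 10 unilateral, 10 bilateral and 10 control patients, with the controls case-matched on age at surgery and body surface area. It also mentions comparing the unilateral and bilateral groups with each other.
- **Outcomes, primary:** "A comprehensive cardiac function (i.e. right and left ventricular function, mass, volumes, fibrosis and heart health determined by blood tests) assessment". The components are not ranked.
- **Outcomes, secondary:** "Cobalt and Chromium Ion level measurements in the blood as well as ultrasound of the hip to rule out soft tissue reaction".
- **Analyses, Further Analyses:** the only between-patient analysis is worded as "With the MRI results they will be compared to the Control Group to investigate how both unilateral and bilateral metal on metal implants", with their effect on the heart as its object. Ion levels are not mentioned anywhere in the Analyses section. The closing rule is "Significance will be set to P=0.05 for all findings", with no test, sidedness, order or adjustment.

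**The concern.** A reader of the final report should be able to tell from the plan which single result confirms or refutes the hypothesis. Here three choices are left open:

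1. which question decides (ion correlation, control comparison, or comparison with a normal population);
2. which cardiac measure carries it;
3. which test is used.

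All three could be settled after the data are seen. Because each finding has its own 0.05 threshold and none is labelled exploratory, one nominally significant measure in either metal-on-metal group, in either direction, could be reported as a positive primary finding about cardiotoxicity. Conversely, a null control comparison would leave the stated hypothesis unanswered.

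**Working it through.** **The plan's own figure.** The only figure is the per-test level of 0.05. The plan gives no familywise rate, power, effect size or standard deviation, so there is nothing to reproduce. The question is what the stated rule implies.

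**Inputs from the documents**
- Groups: 10 unilateral, 10 bilateral, 10 control (Recruitment).
- Control contrasts: 2, unilateral and bilateral each against control (Further Analyses). They share the control group, so their statistics for one measure correlate at 0.5.
- Measures: "Measurements of biventricular volumes, function and mass will be derived from the SSFP pulse sequence" (Procedures) gives 3 domains × 2 ventricles = 6. Mean extracellular volume for both ventricles (Heart scan analyses) adds 2, for a total of 8. This count is mine. It leaves out the blood tests (although they are in the primary list), flow measures, oedema, T2*, native T1 and the unilateral-bilateral comparison.

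**Assumptions not in the documents:** two-sided tests, normal data, equal correlation between measures (0 to 0.9 shown, 0.5 to 0.7 taken as central), and the strength of within-pair resemblance due to matching.

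**Simple bounds.** 8 × 2 = 16 tests. Ignoring matching, the expected number of false positives is 16 × 0.05 = 0.8. If all 16 were independent, the chance of at least one would be 1 − 0.95^16 = 56.0%.

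**Simulation under no true effect.** There were 40,000 runs per scenario (standard error at most √(0.25/40,000) = 0.25 percentage points). Each contrast uses t = (mean of MoM group − mean of controls) / √(2s²/10), with s² pooled over the three groups. The table gives the chance (%) of at least one p < 0.05 across 8 measures.

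| Reading of the plan | corr. 0 | 0.5 | 0.7 | 0.9 |
|---|---|---|---|---|
| Two control contrasts, matching has no effect | 53.2 | 42.1 | 32.9 | 21.3 |
| Same, within-pair correlation 0.3, unpaired tests | 41.9 | 33.3 | 25.8 | not run |
| Same, within-pair correlation 0.5, unpaired tests | 33.4 | 27.1 | 21.0 | not run |
| One omnibus F test per measure (matching ignored) | 33.4 | 26.0 | 20.4 | 12.9 |
| One ion against each measure, 20 MoM patients | 33.1 | 26.3 | 19.9 | 12.5 |

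A separate run with ordinary two-sample t tests gave 42.4% and 33.3% for the first row at 0.5 and 0.7.

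**Why matching lowers the figure.** Suppose 5 controls are matched to each MoM group (assumed) with within-pair correlation w. In units of σ², the variance of a mean difference is 0.2 − 2 × (5w/100), against the 0.2 that an unpaired test assumes. For w = 0.5 it is 0.15, so the unpaired test needs 1.96/√0.75 = 2.26 true standard errors and runs at about 2.4% per contrast. For w = 0.3 it is 0.17, needs 1.96/√0.85 = 2.13, and runs at about 3.4%.

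**Sensitivity, matching ignored**
- Left and right versions of a measure correlated 0.7-0.9 and different measures 0.2-0.5: 36-45% for two contrasts.
- Adding the four flow quantities (12 measures): 52.0% at 0.5 and 39.8% at 0.7.
- Adding unilateral versus bilateral (24 tests, normal approximation): 50.7% and 40.1%.
- Counting only the adverse direction (all measures signed alike, assumed) at 0.5 to 0.7: 16-22% for two contrasts and 10-13% for the ion correlation, against 2.5% for one test.

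**Cutting the measures alone.** With one lead measure, two unadjusted control contrasts give about 9% if matching has no effect. Under the matching assumptions above they give about 5-7%.

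**The case against.** - **This is a small preliminary study.** It has 30 patients and no power claim, and its stated purpose is descriptive. A per-test threshold does not promise familywise control. This is fair, and it weakens the percentage as the main argument. But no section labels any result exploratory, and the plan sets a significance threshold for every finding. If exploratory work is meant, saying so is part of the remedy. The Outcomes section's reference to post-hoc T1 mapping does not help here, because it describes image processing after acquisition.
- **The ion analysis is not absent.** A reader might infer that the hypothesis has no analysis at all. The documents do not support that: the Hypothesis gives form and direction, and Recruitment states the intent. What is missing is a specified analysis. Listing ion levels as secondary is also weak evidence of contradiction, because a secondary measurement can still serve as the predictor.
- **The count, the correlation and unmatched tests are not the plan's.** This stands. It is why the matched range must be shown beside the unmatched one, and why no single percentage describes the plan.
- **One primary measure is a preference.** Partly so. A fixed order or Holm adjustment would also control error. Bonferroni over the 16 unmatched tests (0.05/16 = 0.0031) gives 3.9% at correlation 0.5 and 3.2% at 0.7, by normal approximation. None of these says which question is primary.

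**Conclusion.** The point holds and should be settled before analysis. On the text alone, the primary outcome has no lead measure, the only hypothesis has no specified analysis, and 0.05 is applied to everything without a test, order or adjustment.

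The size depends on assumptions. For 8 MRI measures correlated 0.5-0.7, the chance of at least one false positive is about 33-42% for two control contrasts if matching has no effect. It is about 21-33% if within-pair correlation is 0.3-0.5 and unpaired tests are used. It is about 20-26% for one omnibus test per measure, or for one ion against each measure in 20 patients.

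Two stronger readings should be resisted. A reader might take 33-42% as the plan's error rate, but that sets aside the case-matching in Recruitment. A reader might also infer that every way of testing several measures is far above 5%. That fails in favourable corners: with 8 measures, a pooled MoM-versus-control unpaired test and within-pair correlation 0.5, the chance is 8.4% at measure correlation 0.7 and 5.1% at 0.9. The gap between hypothesis and analysis remains whichever percentage applies.

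**What to change.** Before analysis, replace the sentence setting the significance level with:

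> The primary measure is [one cardiac measure chosen by the sponsor]. The primary test is its correlation with [one ion] in the 20 metal-on-metal patients (the stated hypothesis), two-sided 0.05. All other measures, the unilateral, bilateral and control comparisons, and the other ion are reported as estimates with 95% confidence intervals and labelled exploratory; comparisons with control take account of the case-matching on body surface area and age at surgery.

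If the sponsor prefers the control comparison as primary, it should name one test that accounts for the matching and reword the Hypothesis to agree. Matching matters here: for one measure, a pooled unpaired test would run at about 3% (within-pair correlation 0.3) or 1.8% (0.5) instead of 5%, which wastes power with only 10 controls.

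**Cost:** wording in the Hypothesis, Outcomes and Analyses sections and one sponsor decision, with no extra patients, scans or blood draws. The downside is that non-primary measures can no longer be claimed significant at an unadjusted 0.05, so an effect confined to one of them could be reported only as exploratory. The primary correlation also has limited reach: by Fisher's z, 80% power at n = 20 needs a correlation of about tanh((1.96 + 0.84)/√17) = 0.59 in absolute size.
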